### **Preexisting Condition**

A preexisting condition is one that is present at the start of the study. A preexisting condition should be recorded as an adverse event if the frequency, intensity, or the character of the condition worsens during the study period.

### **General Physical Examination Findings**

At screening, any clinically significant abnormality will be recorded as a preexisting condition. At the end of the study, any new clinically significant findings/abnormalities that meet the definition of an adverse event will also be recorded and documented as an adverse event.

### **Post-study Adverse Event**

All unresolved adverse events should be followed by the investigator until the events are resolved, the subject is lost to follow-up, or the adverse event is otherwise explained. At the last scheduled visit, the investigator should instruct each subject to report any subsequent event(s) that the subject, or the subject's personal physician, believes might reasonably be related to participation in this study.

The investigator will notify the drug manufacturer, IRB, and FDA of any death or adverse event occurring at any time after a subject has discontinued or

terminated study participation that may reasonably be related to this study. The drug manufacturer, IRB, and FDA will also be notified if the investigator should become aware of the development of cancer or of a congenital anomaly in a subsequently conceived offspring of a subject that has participated in this study.

### **Abnormal Laboratory Values**

A clinical laboratory abnormality should be documented as an adverse event if any one of the following conditions is met:

- The laboratory abnormality is not otherwise refuted by a repeat test to confirm the abnormality
- The abnormality suggests a disease and/or organ toxicity
- The abnormality is of a degree that requires active management; e.g. change of dose, discontinuation of the drug, more frequent follow-up assessments, further diagnostic investigation, etc.

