## **Primary Safety Endpoints**

The primary safety endpoints will be assessed on the adverse events (AEs) and serious adverse events (SAEs) that are observed throughout the trial.

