## **Safety and Adverse Events**

For the purpose of this clinical trial, the National Cancer Institute Common Terminology Criteria for Adverse Events v3.0 (CTCAE), dated December 12, 2003 will be used to grade all adverse events.

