## **Definitions**

### **Adverse Event**

An **adverse event** (AE) is any symptom, sign, illness or experience that develops or worsens in severity during the course of the study. Intercurrent illnesses or injuries will be regarded as adverse events. Abnormal results of diagnostic procedures are considered to be adverse events if the abnormality:

- results in study withdrawal
- is associated with a serious adverse event
- is associated with clinical signs or symptoms
- leads to additional treatment or to further diagnostic tests
- is considered by the investigator to be of clinical significance

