### **Recording of Adverse Events**

At each contact with the subject, the investigator/member of investigator's team will seek information on adverse events by specific questioning and, as appropriate, by examination. Information on all adverse events will be recorded in the source document, and also in the appropriate adverse event module of the case report form (CRF). All clearly related signs, symptoms, and abnormal diagnostic procedures results should be recorded in the source document, though should be grouped under one diagnosis.

All adverse events occurring during the study period must be recorded. The clinical course of each event should be followed until resolution, stabilization, or until it has been determined that the study treatment or participation is not the cause. Serious adverse events that are still ongoing at the end of the study period must be followed up to determine the final outcome. Any serious adverse event that occurs after the study period and is considered to be possibly related to the study treatment or study participation should be recorded and reported immediately.

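### The first laboratory criterion makes any abnormal value not refuted on repeat an adverse event, with no significance filter, and is not reconciled with the general adverse event definition

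*Combined protocol and SAP*

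**What the plan says.** The Primary Safety Endpoints section states: "The primary safety endpoints will be assessed on the adverse events (AEs) and serious adverse events (SAEs) that are observed throughout the trial". It names no metric such as a count, a rate or a proportion of subjects.

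Two sections say when an abnormal result becomes an AE.

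- **Definitions, Adverse Event:** "Abnormal results of diagnostic procedures are considered to be adverse events if the abnormality" meets one of five listed criteria. These are withdrawal from the study, a link to a serious AE, a link to signs or symptoms, extra treatment or testing, and the last, that it "is considered by the investigator to be of clinical significance".
- **Abnormal Laboratory Values:** "A clinical laboratory abnormality should be documented as an adverse event if any one of the following conditions is met". The first condition is "The laboratory abnormality is not otherwise refuted by a repeat test to confirm the abnormality". The second is that the value points to disease or organ toxicity. The third is that it calls for active management.

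Neither section refers to the other. Under Recording of Adverse Events, "All adverse events occurring during the study period must be recorded". Under Safety and Adverse Events, CTCAE v3.0 "will be used to grade all adverse events", but no minimum grade is set for a laboratory value to qualify.

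**The concern.** Each criterion in the Adverse Event definition asks for a consequence, an associated event or sign, or a judgement of significance. The first laboratory condition asks for none of these. Because any one condition is enough, it admits almost every abnormal value that was not overturned, and the second and third conditions then add little. The repeat test does not work as a filter either: a value that a repeat did overturn could still enter through the second condition.

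Two staff members working from different sections could therefore classify the same value differently, and the choice passes straight into the recorded safety data. Treatment is open label, so that choice is made with the arm known. Under Post randomization, both arms have monthly labs, but only the sirolimus arm has weekly labs during conversion. A rule without a clinical filter makes the AE count depend on how often blood is drawn, and that differs by arm.

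**Working it through.** The plan gives no figure for laboratory AEs, so there is none to reproduce. The check has three steps.

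**1. One test case under both lists.** Take a value that is new since baseline, out of range and without symptoms. It is not refuted, leads to no treatment, extra test or withdrawal, has no link to a serious AE, and is judged not clinically significant.

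- Adverse Event definition: none of the five criteria is met.
- Abnormal Laboratory Values: the first condition is met, and one is enough.

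The lists give different answers for this value, and nothing in the protocol says which prevails.

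**2. Possible excess.** Inputs from the protocol are 275 randomized subjects (Randomization), and monthly labs and 4 years of follow-up (Post randomization). The 5% share of panels with such a value is an assumption, as is complete follow-up.

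- Draws per subject: 4 × 12 = 48.
- Panels: 275 × 48 = 13,200.
- Affected panels: 0.05 × 13,200 = 660.
- If each abnormality is confined to one panel: 660 events.
- If each lasts all 48 months and is recorded once: 660 / 48 = 13.75, or about 14 events.

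So the same assumption gives about 14 to 660 extra AEs. Withdrawals would lower these figures. Several analytes per panel could raise them.

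**3. Extra draws in the sirolimus arm.** The length of conversion is not stated, so 4 to 8 extra draws are assumed.

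- 4 / 48 = 8.3% and 8 / 48 = 16.7% more draws.
- Take one analyte, independent draws and a chance p per draw of an unrefuted inconsequential value. The expected number per subject is n × p, and the chance of at least one is 1 − (1 − p)^n. The values of p are assumed.

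| p | n = 48: expected; chance of at least one | n = 52 | n = 56 |
|---|---|---|---|
| 1% | 0.48; 38.3% | 0.52; 40.7% | 0.56; 43.0% |
| 2.5% | 1.20; 70.3% | 1.30; 73.2% | 1.40; 75.8% |
| 5% | 2.40; 91.5% | 2.60; 93.1% | 2.80; 94.3% |

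Counts rise by 8-17% from sampling alone. The proportion of subjects with at least one such value rises by about 2 to 5 percentage points. Values within a subject are correlated in practice, so the table is an illustration and not a forecast.

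**The case against.** A reader might infer that the two sections flatly contradict each other. The text does not go that far. The Adverse Event definition says when an abnormal result counts; it does not say that nothing else counts. It speaks of diagnostic procedures in general, while the other list is specific to laboratory values. The lists can be read as cumulative. That reading stands as possible, but the significance criterion would then have almost no effect for laboratory values, and nothing shows that this was intended.

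The lists also overlap. A repeat ordered to confirm a value is arguably a further test, which already qualifies under the Adverse Event definition. The clear divergence is therefore for inconsequential values that were never repeated, or that were confirmed only at the next routine draw. Applying the first condition to a value never repeated is itself open to argument, since its wording refers to a confirming test. This narrows the point without removing it.

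A reader might also expect chronic out-of-range values to swamp the AE data. The documents do not support that. An AE must arise or get worse during the study, and Preexisting Condition counts a baseline problem only if it worsens. Stable baseline abnormalities are thus arguably excluded. Recording of Adverse Events groups related findings under one diagnosis and follows each event over time, which points away from one AE per abnormal panel. Taking 660 as the expected excess would therefore be wrong; it is the upper end under the stated assumption.

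Finally, more testing in one arm would also find more events under the five general criteria, so detection imbalance is not unique to this condition. That is fair. The first condition worsens it by removing any clinical filter.

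**Conclusion.** The first laboratory condition is too broad as a sufficient criterion and is not reconciled with the Adverse Event definition. The conclusion rests on the wording alone and needs no numerical assumption.

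Its reach is limited to laboratory-based AEs and any AE total that includes them. A reader might infer that the whole primary safety endpoint is undefined. It is not: the serious AE criteria and symptom-based AEs are unaffected, and so is the primary aim on acute cellular rejection.

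The size is unknown. About 14 to 660 extra AEs follows from an assumed 5% of panels and full follow-up. The 8-17% sampling effect in the sirolimus arm follows from an assumed 4 to 8 extra draws. The defect is modest, but it should be settled before AE counts are compared between arms.

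**What to change.** Merge the two lists into one rule, cross-referenced in both sections and applied identically in both arms.

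- Remove the first laboratory condition as sufficient on its own. A laboratory AE then needs at least one of the five criteria in the Adverse Event definition, or the second or third laboratory condition.
- Use the repeat test only to set aside a value shown to be spurious that led to no action. Non-refutation should not become a precondition for every laboratory AE, because that would lose abnormalities that prompted action and then returned to normal.
- State that a value never repeated is judged on the same criteria.
- Record a persistent abnormality as one event.

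The cost is a short wording change and less recording work at the site. The downside is that some low-grade laboratory abnormalities would no longer be recorded as AEs, although the values remain in the laboratory data and can be summarised from there.

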### **Hospitalization, Prolonged Hospitalization or Surgery**

Any adverse event that results in hospitalization or prolonged hospitalization should be documented and reported as a serious adverse event unless specifically instructed otherwise in this protocol. Any condition responsible for surgery should be documented as an adverse event if the condition meets the criteria for an adverse event.

Neither the condition, hospitalization, prolonged hospitalization, nor surgery are reported as an adverse event in the following circumstances:

- Hospitalization or prolonged hospitalization for diagnostic or elective surgical procedures for a preexisting condition. Surgery will **not** be reported as an outcome of an adverse event if the purpose of the surgery was elective or diagnostic and the outcome was uneventful.
- Hospitalization or prolonged hospitalization required to allow efficacy measurement for the study.
- Hospitalization or prolonged hospitalization for therapy of the target disease of the study, unless it is a worsening or increase in frequency of hospital admissions as judged by the clinical investigator.

### **Recording of Adverse Events**

At each contact with the subject, the investigator/member of investigator's team will seek information on adverse events by specific questioning and, as appropriate, by examination. Information on all adverse events will be recorded in the source document, and also in the appropriate adverse event module of the case report form (CRF). All clearly related signs, symptoms, and abnormal diagnostic procedures results should be recorded in the source document, though should be grouped under one diagnosis.

All adverse events occurring during the study period must be recorded. The clinical course of each event should be followed until resolution, stabilization, or until it has been determined that the study treatment or participation is not the cause. Serious adverse events that are still ongoing at the end of the study period must be followed up to determine the final outcome. Any serious adverse event that occurs after the study period and is considered to be possibly related to the study treatment or study participation should be recorded and reported immediately.

### **IRB Notification by Investigator**

Reports of all serious adverse events (including follow-up information) must be submitted to the IRB within 25 days of the investigator/sponsor's knowledge of the event if this event meets UPIRSO criteria. Copies of each report and documentation of IRB notification and receipt will be kept in the regulatory binder for the clinical trial.

### **FDA Notification by Sponsor**

The principal investigator/sponsor shall notify the FDA and study drug manufacturer by telephone or by facsimile transmission of any unexpected fatal or life-threatening experience associated with the use of the drug within 24 hours of the investigator/sponsor's knowledge of the event.

If a previous adverse event that was not initially deemed reportable is later found to fit the criteria for reporting, the principal investigator/sponsor will submit the adverse event in a written report to the FDA and study drug manufacturer as soon as possible, but no later than 15 calendar days from the time the determination is made.

### **Stopping Rules**

Subjects diagnosed with two acute renal allograft rejection episodes post conversion from tacrolimus to sirolimus will be stopped from participating in the study and will be switched back to tacrolimus.

Subjects that develop significant side effects secondary to sirolimus (severe thrombocytopenia (platelets count <50, 000); severe hyperlipidemia not controlled by the use of statins or other cholesterol lowering agents; worsening proteinuria or severe de-novo proteinuria) will have sirolimus stopped and patients will be switched back to tacrolimus.

Subjects developing post-transplant infections (i.e., UTI, CMV, HSV, EBV, HCV, HBV, HIV, PCP), that in the opinion of the investigator are detrimental to the subject and their participation in this research trial, will be stopped from participating in this study.

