## **Treatment of Acute Renal Allograft Rejection**

Initial treatment for biopsy-confirmed acute rejection for all subjects will be pulse corticosteroids (methylprednisolone 500 mg IV x 3 days), tapered to a dose of 20 mg prednisone by day 7, unless the severity of the initial episode warrants use of anti-T-lymphocyte antibody (OKT3 or Thymoglobulin). Recurrent rejection will be treated with anti-T-lymphocyte antibody (OKT3 or Thymoglobulin).

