## **Early Withdrawal of Subjects**

### **When and How to Withdraw Subjects**

Subjects may withdraw from the clinical trial at any time for any reason with no prejudice to their medical care. Subjects may also be stopped in the study without their consent if their medical care requires they be. Also, the Institutional Review Board (IRB) may stop the study at any time and all subjects will be returned to taking tacrolimus and followed for safety. Subjects will be informed of why they are being stopped.

Subjects non-compliant with medications and clinic follow-ups will be withdrawn from the study.

Subjects with post-transplant complications such as malignancy or infections that require modification or withdrawal of maintenance immunosuppression will be withdrawn from the study.

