### **Data Collection and Follow-up for Withdrawn Subjects**

Even though subjects may be withdrawn prematurely from the study, an attempt will be made to collect at least survival data on such subjects throughout the protocol defined follow-up period. Such data is important to the integrity of the final study analysis, since early withdrawal could possibly be related to the safety profile of the study. If a subject withdraws consent to participate in the study, attempts will be made to obtain permission to record at least survival data up to the protocol-described end of subject follow-up period.

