## **Statistical Analysis**

Once the 2 groups of renal transplant patients are identified, two sample t tests will be used to compare differences in continuous variables between groups; chi square tests will be used to compare differences in discrete variables. Multivariable logistic regression analysis will be also performed to identify the combination of clinical variable that are significantly associated with the development of acute rejection and renal allograft function after conversion from tacrolimus →sirolimus.

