### **Adverse Event Reporting Period**

The study period during which adverse events must be reported is normally defined as the period from the initiation of any study procedures to the end of the study treatment follow-up. For this study, the study treatment follow-up is defined as 30 days following the last administration of study treatment.

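### Two rejections after conversion end study participation for sirolimus subjects only, and e-GFR and proteinuria need not be recorded to month 48 afterwards; the effect is probably small and confined to secondary aim i.

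*Combined protocol and SAP*

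**What the plan says.** The Stopping Rules section opens with a mandatory exit: "Subjects diagnosed with two acute renal allograft rejection episodes post conversion from tacrolimus to sirolimus will be stopped from participating in the study". The same sentence switches these subjects back to tacrolimus. Under Randomization, only one arm replaces tacrolimus with sirolimus.

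For repeated rejection in any subject, Treatment of Acute Renal Allograft Rejection gives only a therapy: "Recurrent rejection will be treated with anti-T-lymphocyte antibody". The nearest route out for a tacrolimus subject is a general clause under When and How to Withdraw Subjects: "Subjects may also be stopped in the study without their consent if their medical care requires they be".

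For subjects withdrawn early, Data Collection and Follow-up for Withdrawn Subjects says that "an attempt will be made to collect at least survival data on such subjects throughout the protocol defined follow-up period". Post randomization plans four years of follow-up in both arms, including renal function, but does not say that this continues once a subject has been stopped.

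Secondary aim i (Research Objective) is renal allograft function, measured by e-GFR and proteinuria. For continuous variables, Statistical Analysis states that "two sample t tests will be used to compare differences in continuous variables between groups". It says nothing about subjects who leave and does not name the analysis population.

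**The concern.** The exit is defined by an event that can injure the graft, and it is written for one arm. At time points after exit, the sirolimus arm can lose its double rejecters from the renal-function comparison, while comparable tacrolimus subjects may stay and be measured. If double rejecters have worse function, the remaining sirolimus subjects look better than the arm as randomised. Renal benefit is the rationale for conversion, so a tilt in that direction matters for how aim i is read.

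Values recorded before exit are kept, so early time points lose little or nothing.

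**Working it through.** **Reading the rules together**

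1. *Trigger.* It requires conversion to sirolimus, so a subject who continues tacrolimus cannot meet it.
2. *Matching rule for tacrolimus.* None is mandatory. The rejection-treatment section contains no exit. The other withdrawal grounds (medical need, non-compliance, malignancy or infection) apply to both arms and are not tied to rejection.
3. *Data after exit.* The minimum is an attempt at survival data. More is permitted, but e-GFR and proteinuria are not required.
4. *Adverse-event rules.* Post-study Adverse Event says "All unresolved adverse events should be followed by the investigator until the events are resolved", and Recording of Adverse Events says "The clinical course of each event should be followed until resolution, stabilization". Some renal values around a second rejection may be captured this way. Neither section schedules e-GFR or proteinuria to month 48. This holds whenever the reporting period ends.

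**Illustrating the size**

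The documents give no exit rate, e-GFR deficit or SD, so there is no figure of the plan's own to reproduce.

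Inputs:
- Arm sizes: 275 randomised 2:1 (Randomization) gives about 183 and 92. Sirolimus is taken as the larger arm, as the biopsy counts of about 93 and 46 imply (Biopsy).
- f, the fraction of sirolimus subjects exiting under the rule: 1-3%, assumed. It is kept low because Exclusion Criteria rule out recent rejection and more than two earlier episodes. Exits: 183 × 0.01 to 183 × 0.03 = 1.8 to 5.5, about 2-5 subjects.
- d, the e-GFR deficit of those subjects against those who stay: 10-30 mL/min, assumed.
- SD of e-GFR: 20 mL/min, range 15-25, assumed.

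Bias: if stayers have mean μ, the full-arm mean is (1 − f)μ + f(μ − d) = μ − fd. The mean without leavers is μ, so it is too high by f × d.
- Low end: 0.01 × 10 = 0.1 mL/min.
- High end: 0.03 × 30 = 0.9 mL/min.

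Standard error of the arm difference: SD × √(1/183 + 1/92).
- SD 15: 1.92. SD 20: 2.56. SD 25: 3.20.
- At SD 20 the bias is 0.1/2.56 = 0.04 SE to 0.9/2.56 = 0.35 SE.
- The high end is 0.9/1.92 = 0.47 SE at SD 15 and 0.9/3.20 = 0.28 SE at SD 25.

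Error rate of a nominal two-sided 5% test when the bias is k standard errors: Φ(−1.96 + k) + Φ(−1.96 − k). k = 0.04 gives 5.0%; k = 0.35 gives 6.4%.

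Sensitivity:
- Tacrolimus double rejecters equally frequent with the same deficit, and half of them also withdrawn: net bias f × d × 0.5 = 0.05-0.45 mL/min.
- Month 24, exits spread evenly over 48 months, no tacrolimus loss: f × d × 24/48 = 0.05-0.45 mL/min.
- Exit rate 5%: 0.05 × 10 to 0.05 × 30 = 0.5-1.5 mL/min, or 0.20-0.59 SE at SD 20.
- If the 70% biopsy fraction implies a smaller trial (93/0.7 = 133 and 46/0.7 = 66), f × d is unchanged, the SE at SD 20 is 3.01, and the bias is 0.03-0.30 SE.

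**The case against.** The strongest reply is that the effect is small and every input to its size is assumed. The 6.4% error rate needs the worst corner of the main range at SD 20: 3% exiting, a 30 mL/min deficit and no tacrolimus loss. This stands, and it is why the point is minor.

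The survival-data wording is also a floor. At a single centre with monthly routine labs, renal values may well be kept. That stands too: a reader might infer that e-GFR will be lost after exit, but the text shows only that it need not be recorded.

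A reader might also cite Adverse Event Reporting Period, where "the study treatment follow-up is defined as 30 days following the last administration of study treatment", and conclude that all capture ends 30 days after exit. The documents do not settle this. Tacrolimus and MMF are themselves listed under Study drugs, and the subject returns to tacrolimus, so the last study treatment need not fall at exit. Lasting graft dysfunction could also remain an open adverse event for a long time. Neither point creates a scheduled month-48 value.

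Finally, f × d is a bias only if values after the switch back belong to the sirolimus arm. The plan names no estimand, so the calculation applies to an as-randomised comparison. That is the natural reading of a randomised trial, but it is not written down.

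**Conclusion.** The asymmetry is real and comes from a stated rule. Two rejections after conversion are a mandatory exit that only sirolimus subjects can meet, and the required data after exit do not include e-GFR or proteinuria. In an as-randomised comparison on secondary aim i, this can favour sirolimus at later time points if double rejecters have lower e-GFR. Under the assumed 1-3% exit and 10-30 mL/min deficit, the size is 0.1-0.9 mL/min, at most about 0.35 SE at SD 20, and smaller if tacrolimus double rejecters also leave.

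Three stronger readings are not supported:
- *The primary result is biased.* A subject who exits under this rule has already had two rejections, so a count of first rejections is unaffected. Only later episodes, if counted, could be missed.
- *Tacrolimus double rejecters always stay.* They can be withdrawn at discretion; no rule requires it.
- *Subjects switched back for sirolimus side effects are lost as well.* Stopping Rules orders their switch but does not say whether they remain in the study.

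The text also leaves open whether survival data includes graft status. Severity: minor.

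**What to change.** Three edits:

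1. *Stopping Rules, first sentence.* Replace the words that end participation with: *will stop sirolimus and all research blood, urine and biopsy sampling*. Keep the switch back to tacrolimus, which is the protective step.
2. *Data Collection and Follow-up for Withdrawn Subjects, first sentence.* Replace the survival-data minimum with: *at least patient survival, graft status, and e-GFR and proteinuria from routine clinic labs where available, to month 48*. Leave the sentence on withdrawal of consent unchanged.
3. *Statistical Analysis.* State that renal-function comparisons are by randomised arm and include these values.

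Cost: one amendment through the IRB (Ethical Considerations) and chart data entry. The second edit covers subjects withdrawn for any reason in both arms. The documents do not give their number; double rejecters would account for about 2-5 under the assumed rates. No research visits or tests are added. Some non-attenders will have no labs to enter, and proteinuria will exist only where routine care measures it. Values after the switch back reflect tacrolimus treatment but count in the sirolimus arm, which the report should state.
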